12.3 Blinding considerations

No blinded randomized controlled trial comparing early-ablation strategies to cardioversion-led strategies has been performed. For a procedure whose primary purpose is to give sustained symptomatic relief, definitive quantification of the true placebo-controlled effect size of AF ablation is necessary. The present study was designed to address the lack of clinical research / lack of evidence-based practice in this area.

12.3.1 Rationale for blinding

The rationale for blinding where possible in clinical trials is well established, and discussed in Introduction (Section 5.4).

Placebo effects and distorted participant reporting appear to be greater in surgical trials than in drug trials. There are many factors involved in surgical procedures such as hospitalization, ancillary treatments, the surgical ritual itself or the technology used that can all heighten the placebo effect. Correcting for placebo effects is becoming more important as more subjective 'soft' outcome measures are used eg. Quality of Life (which are more prone to be influenced by placebos).

The magnitude of the placebo effect may be a critical factor in determining the outcome of a trial. A difference between two treatments such as DCCV and PVI might result from differences in their placebo effects so it is important to blind patients to the intervention they have received.

Specific emphasis will be placed on this being a blinded trial. Patients will be informed that they may receive an electrical cardioversion with or without pulmonary vein isolation procedure. The procedure performed will be determined at random following administration of sedation and insertion of groin sheaths under ultrasound guidance. Patients will not be informed which procedure they have undergone until the end of the trial period or the study end-point whichever is sooner. Patients who undergo a cardioversion only who revert to persistent AF will be offered a pulmonary vein isolation procedure if indicated as standard medical care under current guidelines.

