7.2 Exclusion criteria

Patients who meet the following exclusion criteria will be ineligible for study participation;

- Creatinine clearance (eGFR) < 30mls/min
- Contraindication or unable to take anticoagulation
- Contraindication or unable to tolerate amiodarone
- Uncontrolled hypertension
- Contraindication or catheter ablation
- BMI > 35

8. Study design

Barts Health patients referred from other Barts Health NHS Trust Hospitals (Homerton, Chase Farm, Barnet) for either cardioversion for persistent AF or catheter ablation of persistent AF will be approached for recruitment.

- All patients:
 - Patient drug treatment will follow local clinical guidelines for AF ablation and be recorded in the CRF.
 - Patient baseline characteristics recorded at preadmission
 - Estimated AF duration
 - LA dimensions (Echocardiogram)
 - Ejection fraction
 - Routine Bloods

- Creatinine & Electrolytes,
- Full blood count,
- Thyroid function
- Quality of Life measures
- BP
- CHADS VASC score / assessment
- Medical History and Comorbidities
- Demographics (Age, sex, ethnicity)
- Physical exam (BP, HR, Weight, Height, BMI)
- Medications
- Day of Procedure – blinded randomisation to intervention (DCCV, or Pulmonary Vein Isolation plus DCCV). Reveal LINQ inserted during procedure.
- 6 weeks: QoL measures, telephone FU
- 3 months: Clinical follow up, 12 lead ECG, Repeat QOL measures
- 12 months: Clinical follow up, Endpoints measured. Once subject participation in the trial is complete, the patient and physician will be unblinded. If the patient is in AF, management of AF proceeds as clinically indicated.
- All patients who consent to have data capture continue in AF registry for 5 years.

The pilot study patients will be analysed at 3 months and 12 months to allow assessment of feasibility of a larger trial, and patients who complete the 12 month follow-up visit and consent will continue in registry follow-up for 5 years post procedure.

9. Study procedures

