9.6 Blinding procedures

The aim of blinding will be to prevent patients, their treating clinicians and their treatment choices being influenced by knowledge of the procedure being performed. The pilot study will establish the effectiveness and feasibility of blinding procedures. Patients will be admitted to the day ward for "Orbita AF DCCV±ablation". They will undergo confirmation of study and procedural consent by a senior cardiology fellow/registrar or consultant. Patients will be accompanied to the cath lab by a clinical fellow or research nurse (Chaperone), and at this point their care will be transferred to the cath lab team. The patient will enter the catheter lab and standard AF preprocedural checks will be performed. Patients will be offered to wear headphones playing relaxing music of their choice during the procedure. A groin access / draping pack will be opened for all patients and sedation given. After GCS < 10, the patient will be randomised to either DCCV and ablation, or DCCV alone using REDcap (mobile app). The procedure will be performed according to protocol. At the end of the procedure, a "sign out" will be performed, where the procedure performed is confirmed to the operating team. Here the randomised allocation will not be specified in keeping with the blinding SOP. If no complications occurred, the procedure performed will not be specified on sign-out, hand over to the ward staff will be as follows:

"A DC cardioversion plus or minus Cryoablation under the study protocol was performed with groin sheath access and no complications. The patient should be managed assuming they have undergone an ablation procedure".

Patients who are accidentally unblinded will be withdrawn from the trial.

Patients will complete a questionnaire immediately prior to discharge to establish their perception of which procedure was performed.

Randomisation will be performed in a 1:1 ratio, between 3 and 4 patients per day will have procedures performed as per this protocol. Individual randomisation will be performed after insertion of groin sheath and administration of sedation.

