16.1 Devices

Loop recorder	• Manufacturer: MEDTRONIC LTD
----------------------	-------------------------------

	
 • Indication : Long-term monitoring of heart rhythm. Determination of duration of AF episodes and confirmation of primary endpoint • CE Mark : Yes • Source of Device : Medtronic Ltd In-kind research grant contribution • How device used : The Reveal device is inserted in the prepectoral position under the skin. This is performed with local anaesthetic in the preadmission clinic by a trained nurse or doctor. The device will provide a continuous recording of the heart rhythm and rate, and will be able to download duration of AF episodes via a home monitoring system to establish the primary endpoint of the study.
Cryoballoon, Cryocath, Achieve wire, Console and related items	
 • Manufacturer: MEDTRONIC • Indication: AF ablation catheter and sheath • CE Mark: Yes • Source of Device: Clinical use for AF ablation • How device used: The cryoballoon is the key specified technique for performing pulmonary vein isolation in the ablation arm in this trial. This allows the physician electrophysiologist to perform a circumferential freeze around the pulmonary veins to electrically isolate the vein, thus preventing pulmonary vein ectopy from triggering arrhythmia.

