17.5 Notification and reporting of Serious Adverse Events

Serious Adverse Events (SAEs) that are considered to be 'related' and 'unexpected' will be reported to the sponsor within 24 hours of learning of the event, and to the REC within 15 days in line with the required timeframe.

The treatment code for the participant will be broken when reporting an 'unexpected and related' SAE. The unblinding of individual participants by the PI / CI in the course of a clinical study will only be performed if necessary for the safety of the study participant.

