6.1 Design

ORBITA-AF feasibility study is an internal pilot study. It is a randomised blinded controlled trial at two sites. Patients will be randomised to receive DCCV+PVI or DCCV alone. No information about the procedure will be transferred from catheterisation laboratory (cath lab) staff to recovery staff and cath lab staff will have no further contact with the patient during the study. Patients and other healthcare professionals will remain blinded to treatment allocation. If a future trial is determined to be feasible and no major changes to the design have been made from this pilot study, then pilot study patients will be included in the future main trial. This pilot study aims to recruit 20 patients.

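### The relapse offer in Protocol 12.3.1 is worded by arm and untimed, so making it during follow-up would reveal allocation before the SAP's 12-month quality-of-life scores

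*Protocol*

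**What the plan says.** Two consecutive sentences of Protocol 12.3.1 matter. The first sets the time of disclosure: "Patients will not be informed which procedure they have undergone until the end of the trial period or the study end-point whichever is sooner". The second is the relapse offer: "Patients who undergo a cardioversion only who revert to persistent AF will be offered a pulmonary vein isolation procedure if indicated as standard medical care". The protocol does not define the study end-point. The offer has no date, and 12.3.1 does not mention PVI patients who relapse.

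Other places bear on the same question:

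- Protocol Section 8, under the 12-month visit: "Once subject participation in the trial is complete, the patient and physician will be unblinded. If the patient is in AF, management of AF proceeds", that is, according to clinical need. This covers both arms.
- Protocol 9.6 says that blinding is meant to "prevent patients, their treating clinicians and their treatment choices being influenced by knowledge of the procedure being performed".
- Protocol 17.5 breaks the code for an unexpected and related SAE. Otherwise, unblinding by the investigators during the study "will only be performed if necessary for the safety of the study participant".
- SAP 6.1: "Patients and other healthcare professionals will remain blinded to treatment allocation".
- SAP 6.4.2, 6.4.3 and 6.4.5 place SF-12 and AF-PROMS at 12 months. The protocol's own schedule (9.4) marks quality of life only at screening, 6 weeks and 3 months, and SAP 7.1.1 lists only symptoms at 12 months.

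Protocol 9.3.4 refers to a study-specific blinding SOP, which was not available for this review.

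**The concern.** An offer that depends on the arm can be made only by someone who knows the arm, and a patient who receives it learns the arm. A relapsing patient who is not offered PVI may infer the other arm, if patient or clinician knows the rule. If this happens before month 12, disclosure is triggered by the outcome and is more frequent where relapse is more frequent.

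The 12-month SF-12 and AF-PROMS change scores are the most exposed. Section 12.3.1 itself argues that soft measures such as quality of life are more open to placebo effects, and 12.3 gives a placebo-controlled effect size as the reason for the trial. In patients who then have rescue ablation, its real effect could not be separated from the effect of knowing the arm. Outcomes that depend on clinicians' decisions (repeat procedures, antiarrhythmic drug use) are exposed after disclosure too.

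**Working it through.** **Step 1. When may allocation be told?** Section 8 places it after the patient's participation is complete. In 12.3.1 it depends on what the study end-point is. The schedule in 9.4 heads each patient's last clinic visit as 12 months/EOS, Section 8 measures endpoints there, and 9.8 ends the study at the last patient's 12-month visit. If the study end-point is the patient's own 12-month visit, 12.3.1 and Section 8 agree.

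**Step 2. Does the plan expect ablation of DCCV patients before month 12?** It appears to:

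- Repeat procedures are a secondary endpoint (Protocol 6.4), counted within 12 months (SAP 6.4.2, 6.4.5).
- Protocol 11.2 estimates 25-30% cross-over from DCCV to ablation. SAP 6.4.4 restricts cross-over to the index procedure, so this supports the inference but does not prove it.
- Protocol 9.3.4 allows for a patient unblinding event before the end of the study.

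So whichever meaning the study end-point has, the arm-worded offer can fall within follow-up and would then work against 9.6 and Section 8.

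**Step 3. The plan's own figures (Protocol 11.1).** Recurrence at one year is 47% for ablation and 66% for DCCV.

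- HR = ln(1 - 0.66) / ln(1 - 0.47) = 1.70, as stated.
- Freedman's formula, two-sided 5%, 80% power: 117 events. Mean event rate (0.47 + 0.66)/2 = 0.565, and 117/0.565 = 207.1, so 104 per group, as stated. Schoenfeld's formula gives 112 events and 100 per group.
- For 0.4 SD in a continuous outcome, 99 per group are needed for 80% power; 104 give 82%.

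**Step 4. Ceilings on patients who learn their arm at relapse.** This assumes that the planned rates apply to the trial's definition of recurrence.

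| | DCCV | PVI |
|---|---|---|
| Pilot | 10 x 0.66 = 6.6 | 10 x 0.47 = 4.7 |
| Main trial | 104 x 0.66 = 68.6 | 104 x 0.47 = 48.9 |

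The gap is 66 - 47 = 19 percentage points. If only patients offered PVI learn their arm, the ceilings are 66% and 0%. If the 25-30% cross-over estimate stands in for the DCCV share, 2.5 to 3 of 10 pilot patients and 26 to 31 of 104 main-trial patients would be affected.

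**Step 5. Scale only.** Suppose a share s of the DCCV arm and nobody in the PVI arm is told. The mean reporting shift per told patient that would move the arm difference by 0.4 SD is 0.4/s:

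| s | Basis | Shift needed |
|---|---|---|
| 0.66 | every DCCV relapser (extreme case) | 0.61 SD |
| 0.33 | half of them | 1.21 SD |
| 0.30 | upper cross-over estimate | 1.33 SD |
| 0.25 | lower cross-over estimate | 1.60 SD |

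Smaller shifts move the difference in proportion. The documents give neither s nor the shift, so this is not an estimate of bias.

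**The case against.** A reader might infer more: that the study end-point is the patient's own AF episode of more than 7 days, so that 12.3.1 schedules unblinding at relapse in direct conflict with 17.5 and SAP 6.1. There is some support. Section 16.1 says the recorder "will be able to download duration of AF episodes via a home monitoring system to establish the primary endpoint of the study", and the sentence after the disclosure rule turns to relapse. The documents do not settle it. Under the 12-month reading, the whichever-is-sooner clause still has a use: a patient need not wait for the last patient's visit. Section 17.5 sits within SAE reporting and is not a general timetable for disclosure. SAP 6.1 gives no duration of blinding. The SAP was written from protocol version 2.0 of 25/06/2019, while the signatures in this protocol are dated 12 February 2019, so a conflict between the two documents is not secure.

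Other points against also carry weight. Section 8 already has arm-neutral wording for AF care. Section 12.3.1 is an ethics rationale, and its offer applies only if indicated as standard care. The blinding SOP may settle the matter. The pilot tests no hypotheses. Blinding success is itself a progression criterion, and the move to the main trial needs an REC amendment anyway.

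These points lower the severity but do not remove the arm-worded, untimed offer. If staff follow it during follow-up, it reveals allocation whatever the study end-point means. Section 8's neutral sentence applies only after participation ends, so it gives no rule for relapse before then.

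**Conclusion.** A cheap improvement: minor for the 20-patient pilot, and worth making because SAP 6.1 would carry pilot patients into the main trial if the design does not change in a major way. The protocol lacks an arm-neutral rule for relapse during follow-up, and its disclosure time is ambiguous.

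The conclusion assumes that some PVI offers are made before month 12, which the plan appears to expect but does not state. It also assumes that 12-month quality of life is collected as most of the SAP says, although the protocol schedule does not show it, and that the blinding SOP does not already close the gap.

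The 66% and 47% are upper limits. The true shares are unknown because the offer is conditional and untimed. The documents support no figure for quality-of-life bias, and the 0.61 SD extreme case should not be read as one. The primary endpoint is largely unaffected: it comes from the recorder, and for a patient told after a qualifying episode it is already fixed.

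**What to change.** 1. In Protocol 12.3.1, replace the arm-specific sentence with a neutral one, for example: *patients in either group who revert to persistent AF will have AF management as clinically indicated, without reference to allocation*. Replace the undefined study end-point with Section 8's timing: allocation is told after the patient's own 12-month assessments, except for safety.
2. If allocation must be disclosed earlier for clinical care, collect SF-12, AF-PROMS and the blinding guess just before, and record the date. State that such a patient is not withdrawn under 9.6 (and so not replaced under 9.10) and stays in 12-month intention-to-treat follow-up. Report the number disclosed by arm.

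The cost is a protocol amendment, a date field, a line in the SAP's reporting and one event-triggered questionnaire contact per patient disclosed early. At the ceiling that is 6.6 + 4.7 = 11.3 of 20 pilot patients and 68.6 + 48.9 = 117.5 of 208 in the main trial. If disclosure waits for the 12-month assessments, there are no extra contacts.

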12.4 Specific procedural considerations

All patients having either a DCCV or AF ablation are given conscious sedation or general anaesthetic.

An AF ablation is performed using transeptal puncture using standard techniques. The risks associated with a transeptal puncture are very low. Groin access complications are around 1% and even less with ultrasound guidance (0.2%).

The DCCV only group would require the patients to have a line put in, which is not normally done. However, this venous access could be used for the administration of anaesthetic and sedation agents, and for fluids if required. This will allow the patients to be effectively blinded to which procedure they have received and allow the specific effects of the AF ablation to be measured.

The risks and harms to the patient of a transeptal puncture are very low and patients who are suitable for an AF ablation (i.e. all patients eligible for the trial) would require this access for the procedure to be performed. The risks have been minimised by using ultrasound guidance for the venous access.

The risks of this procedure also need to be balanced against the risks associated with the patient being maintained on medications to reduce their risk of arrhythmia.

Subjects are free to withdraw from the study at any time, without providing a reason. If the subject asks the investigator to destroy all identifiable samples taken from the subject and/or not enter into the CRF results of the follow-up examination, the investigator will comply with the subject's requests.

The CI will ensure that the REC is informed promptly of any serious adverse event that occurs during this study and that is both related and unexpected (see section 13), in line with NRES SOPs, and will provide the REC with annual progress reports of the study, if it lasts longer than a year.

12.5 Annual Safety Reporting

The CI will send an Annual Progress Report to the REC and the sponsor using the HRA template on the anniversary of the REC "favourable opinion".

13. Public Involvement

We have obtained input from our patient volunteers at the William Harvey Heart Centre and from the Trials Connect patient group. They have reviewed our patient facing literature (PIS and ICF) and had input into our trial design. This has ensured that our proposal, particularly the lay summary, is understandable to our patient population. We have also had input from our AF patients treated at our Trust. We will also include a patient representative on our Trial Steering Committee.

14. Data handling and record keeping

14.1 Data management

A REDCap database will be designed by CVCTU to capture the study data. The eCRFs will have an audit trial, will have electronic signatures, users will have specific access

and user rights, and they will enable real-time data clarifications and cleaning, and data exports and analysis. All source documents will be kept securely in the participant study files or Investigator Site File (ISF) within locked cabinets in restricted access rooms within the Barts Health Centre. The CVCTU will maintain the Trial Master File (TMF), and provide trial management support and tracking for recruitment, data capture, monitoring and safety reporting.

14.2 Source data

Source data are the original forms of data used in the study. Some source data will be generated directly by the study (e.g. ablation reports, questionnaire responses) while others may need to be collected from other 'source documents' (e.g. a participant's medical history in their case notes for inclusion). All source data will be collected by the Investigator or delegated member of the research team, filed in a participant study file (which will include study documents such as the consent form, inclusion and exclusion criteria, cardioversion and ablation reports, AEs, medication records, EQ5D questionnaire etc), and source data will be captured in an electronic database (REDCap). A Source Data Agreement will be completed to determine what is considered as the 'source' data for the trial.

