9.3.4 All patients

Recovered to ward. 12 lead ECG performed but not shown to patient. Patient mobilised and discharged after 4 hours.

Blinding

There is a study specific Standard Operating Procedure on the blinding procedure used in this study. No information on the procedure given will be transferred from cath lab staff to the recovery ward staff.

Patients and other healthcare professionals will also be blinded to which treatment the patient received. The cath lab staff performing the procedure will have no further contact with the patient during the study. A 'chaperone' will be assigned for each patient, who will take over from the cath lab staff in caring for the patient post intervention.

A standard procedure report will be used for clinical records, with a procedure report entered into the study database. This will be transferred to the clinical database at the end of the study or at a patient unblinding event, whichever is earlier.

In the present study we will use a modification of the blinding procedure used in the ORBITA trial (Al-Lamee et al., 2018). A specific blinding questionnaire will be used at the end of the day of the intervention asking the patient and ward staff to guess the treatment allocation. As is typical of AF studies involving ablation, a blanking period will be observed. This accounts for the frequent recurrence of arrhythmia in the days following ablation, where healing atrial tissue can be vulnerable to arrhythmia which is not predictive of longer-term outcome. At the end of the blanking period (ie. 6 weeks) patients will be asked to complete the blinding questionnaire again. This blinding index will be reported on the day of the intervention and at 6 weeks and 3 months follow up to allow the degree of blinding to be assessed.

[figure not shown]

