14.3 Confidentiality

The Principal Investigator has a responsibility to ensure that participant anonymity is protected and maintained. They must also ensure that their identities are protected from any unauthorised parties. Information with regards to study participants will be kept confidential and managed in accordance with the Data Protection Act, the General Data Protection Regulation (GDPR), NHS Caldecott Principles, the UK Policy Framework for Health and Social Care Research, and the conditions of Research Ethics Committee favourable opinion. All research team members have undergone GCP training. The Chief Investigator and the study team will adhere to these parameters to ensure that the Participant's identity is protected at every stage of their participation within the study.

Following consent and during the study, all participant study records and samples will be marked by a single, unique pseudoanonymised identifier. The code for the pseudoanonymised will be kept on a study ID log with the ISF, which will be kept within a locked filing cupboard within a locked room that only the researchers involved have access to. A paper record of any information will be coded and any patient identifiable information (PID) will be removed e.g. name, date of birth and NHS number.

Personal information will only be used on the consent form and the pseudoanonymisation code (screening log). Personal information will be used by the site study team to contact participants if needed and to remind participants of study dates. Fully anonymised data will be shared with fellow researchers via conference presentation and via publication of the results in scientific journals. Pseudoanonymised data will be shared between the research teams named in the application, and access will be granted to members of the Sponsor and Barts CVCTU teams for the purposes of data monitoring and audit.

Only the clinical care team will have access to clinical case notes, which have identifiable personal information for the purposes of identifying potential participants.

The research team will create a separate study file for each participant which will comprise of information given by the participant at the time of screening and during

visits. Routine biochemistry will be measured in Barts Health NHS Trust clinical laboratory by the laboratory biochemists.

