The Investigator Site File (ISF) and subject study files will be kept in a locked cupboard in a locked room that only the researchers involved have access to. The Trial Master File (TMF) will be maintained and stored by the Barts CVCTU in the William Harvey Heart Centre, in a locked room with restricted access.

Under no circumstances will non-encrypted named data be placed on a laptop computer, portable storage device (memory stick or CD-ROM) or transferred by email.

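### Protocol 14.2 files the cardioversion and ablation reports with the follow-up records, leaving research staff who conduct follow-up a route to the allocation that no blinding-role rule controls

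*Protocol*

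**What the plan says.** Protocol 14.2 counts ablation reports among the source data that the study generates. It says that "All source data will be collected by the Investigator or delegated member of the research team" and that the data are "filed in a participant study file (which will include study documents such as the consent form, inclusion and exclusion criteria, cardioversion and ablation reports". The list runs on in the same file: "cardioversion and ablation reports, AEs, medication records, EQ5D questionnaire etc".

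Protocol 14.3 describes the participant file differently. Its wording on the contents is "create a separate study file for each participant which will comprise of information given by the participant at the time of screening and during", where the sentence goes on to the trial attendances; procedure reports are not mentioned. On access, it says that "subject study files will be kept in a locked cupboard in a locked room that only the researchers involved have access to".

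The blinding text points the other way. In Protocol 9.3.4, "Patients and other healthcare professionals will also be blinded to which treatment the patient received". The clinical record carries a standard report, and a procedure report goes into the study database. Of the latter the protocol says: "This will be transferred to the clinical database at the end of the study or at a patient unblinding event, whichever is earlier". SAP 6.1 repeats the commitment: "Patients and other healthcare professionals will remain blinded to treatment allocation". Protocol 8 unblinds the physician only when the patient's participation is over.

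**The concern.** Protocol 9.3.4 treats the procedure report as something that gives the arm away, which is why it is held back from the clinical database. Protocol 14.2 then puts the cardioversion and ablation reports in the file where follow-up records are kept. A member of the research team who opens that file to add an adverse event, a medication change or a questionnaire could see which procedure was done.

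Protocol 9.6 says that blinding is meant to keep treating clinicians and their treatment choices free of that knowledge. Follow-up staff who know the arm may judge the relatedness of an event differently, put questions differently, or influence decisions on further procedures and drugs. The pilot is also meant to establish whether the blinding works, and under SAP 6.1 its patients may be carried into the main trial.

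**Working it through.** No figure in the plan bears on this point, so the check sets the texts on filing, access and blinding side by side.

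1. **What reveals the arm.** Ablation is done only in the DCCV + PVI arm (Protocol 9.3.2 and 9.3.3). An unmasked ablation report in a file therefore identifies the arm, and its absence suggests the other. This is an inference, but the delayed release in 9.3.4 rests on the same reasoning.

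2. **Where it is filed.** Protocol 14.2 puts it in the participant study file with adverse events, medication records and a questionnaire. Nothing in either document says that it is sealed, masked or stored apart.

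3. **Who can open the file.** Protocol 14.2 gives collection to the investigator or a delegate, and 14.3 gives access to the researchers involved. Neither distinguishes blinded from unblinded staff.

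4. **Who is meant not to know.** Patients and healthcare professionals outside the cath lab (Protocol 9.3.4, SAP 6.1), treating clinicians (Protocol 9.6), and the physician until participation ends (Protocol 8).

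5. **How far each written safeguard reaches.**
   - Standard report and delayed release (9.3.4): the clinical records and clinical database.
   - User-specific rights (14.1): REDCap, and not tied to blinding role.
   - Locked cabinets, cupboard and room (14.1, 14.3): people outside the team.
   - No further patient contact for cath lab staff (9.3.4): stops the operators passing on the arm in person, but does not govern the file.
   - Unblinded investigator (SAP 7.4): names a role at randomisation, but does not limit the file to it.

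   None of these covers the participant file by blinding role.

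6. **Which endpoints are exposed.**
   - More exposed: procedure-related complications, which SAP 6.4.5 defines through a judgement of possible relatedness; repeat procedures; antiarrhythmic drug use; and questionnaires that staff administer, including by telephone (Protocol 9.7).
   - Largely protected: recurrence of persistent AF and AF burden, which come from the loop recorder and could be affected mainly through later treatment decisions. Questionnaires that a blinded patient completes alone are also largely protected.

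7. **Whether the pilot would notice.** Protocol 9.3.4 puts the blinding questionnaire to ward staff on the procedure day. SAP Table 2 tabulates a staff index post procedure only, while the patient index is repeated at 6 weeks and 3 months. Staff who learned the arm from the file later would not appear in any planned table.

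8. **Ceiling on opportunities.** Scheduled contacts at 6 weeks, 3 months and 12 months make 3 per patient. Pilot: 3 × 20 = 60. Larger trial, if it goes ahead at 208: 3 × 208 = 624. These count occasions on which a file might be opened, not expected disclosures.

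**The case against.** The case on the other side has real weight.

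- **Unseen documents.** Protocol 9.3.4 cites a study-specific blinding SOP, and 14.2 says that a Source Data Agreement will settle what counts as source data. Either could say where the true report is kept. This stands as a limit on the conclusion, but an explicit filing rule in the protocol should not contradict them.
- **The list in 14.2 is generic.** It is illustrative, and it names EQ5D although the trial's instruments are SF-12 and AF-PROMS. Protocol 14.1 allows source documents to sit in the participant file or the Investigator Site File, and 14.3 mentions no procedure report. So it is not certain which report is filed, where or when. That shows that Section 14 needs reconciling rather than that the filing is safe.
- **Access is controlled.** The files are locked and limited to the team. This is correct; what is missing is a split by blinding role.
- **Treating clinicians work from clinical records.** Those carry the standard report, and nothing says that clinicians consult the research file when choosing treatment. Protocol 12.3.1 also allows patients to be told at the study end-point if that comes sooner, so some repeat procedures may follow planned unblinding. Both points reduce the exposure of treatment decisions.
- **Pilot aims.** SAP 6.5 plans no hypothesis tests. That lowers the inferential stakes, but success of the blinding is itself a progression criterion (Protocol 11.2).

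A reader might infer that outcome assessment is unblinded. The documents do not support that. They name no separate outcome assessor, do not say that follow-up staff read the report, and do not show that an unmasked report is in the file during follow-up.

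**Conclusion.** The point holds as a conflict between a filing rule and the blinding rules. Protocol 14.2 and 14.3, followed as written, give follow-up research staff a route to the allocation that no stated rule closes by blinding role. This runs against Protocol 9.3.4 and 9.6 and SAP 6.1. It should be corrected, but it is not evidence that the blind has failed.

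The size of any bias cannot be derived from the documents. The 60 opportunities in the pilot would all be realised only if every file held an unmasked report and was read at every contact; the 624 also assumes that the larger trial is funded, approved and fully recruited. The concern is confined mainly to endpoints that depend on staff judgement or contact. The conclusion assumes that the blinding SOP and the Source Data Agreement do not already keep the true report apart. If they do, the remaining task is to bring the protocol wording into line.

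**What to change.** Reconcile Protocol 9.3.4, 14.2 and 14.3:

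- In 14.2, take the true cardioversion or ablation report out of the participant study file, and file only the arm-neutral standard report there.
- Hold the true report in a restricted REDCap form or a separate restricted file until end of study or an unblinding event, matching the release rule in 9.3.4.
- State which unblinded roles may open it, and make the access wording in 14.3 and the blinding SOP agree.

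The cost is protocol and SOP wording plus one access setting. The small downside is that monitors must verify the procedure report from a second location.
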